- To compare neonatal and maternal outcomes for women who transfer from home, freestanding midwifery units and alongside midwifery units, during or immediately after labour, with outcomes for women who are not transferred.
- To determine whether indication for transfer, time from decision making until transfer, duration of transfer or events after transfer are associated with poor outcomes for women who are transferred during or immediately after labour.

Methods

Study design

Prospective cohort study with planned place of birth as the exposure and neonatal mortality and morbidity as the primary outcome.

**Note: All comparisons between women who planned to give birth at home or in a midwifery unit and women who planned to give birth in an obstetric unit will be made using planned births in obstetric units as the reference group. This will maximise statistical efficiency and does not imply obstetric units are being considered the standard of care.*

Definitions

Planned birth at home

A birth which occurs for a woman who, at the start of care in labour, intended to give birth at home and who received care from a midwife during established labour at home, regardless of where the woman actually gives birth.

Planned birth in a midwifery unit (freestanding or alongside)

A birth which occurs for a woman who, at the start of care in labour, intended to give birth in a midwifery unit and who received care from a midwife during established labour in a midwifery unit, regardless of where the woman actually gives birth.

Planned birth in an obstetric unit

A birth which occurs for a woman who, at the start of care in labour, intended to give birth in an obstetric unit and who was admitted and received care during established labour in an obstetric unit.

Inclusion criteria

Data will be collected for all women planning birth at home, in freestanding midwifery units and in alongside midwifery units who are attended by a midwife during labour, for any amount of time, in their planned place of birth.

Data will be collected for all women planning birth in an obstetric unit except:

- Women who have an elective caesarean section or any caesarean section before the onset of labour
- Women who present in labour before 36 completed weeks gestation
- Women with a multiple pregnancy

Data will not be collected for women who have an unintended birth at home.

Study sites

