All NHS Trusts providing maternity care in England will be included in the study. The aim is to collect data on every woman planning a home birth in England who has an NHS midwife providing her care. All midwifery units in England, both freestanding and alongside, will be invited to participate in the study. Twenty eight randomly selected obstetric units will be included in the study, stratified by size and geographic location to be representative of obstetric units in England. Data from an ongoing national mapping survey of all NHS Trusts providing maternity care in England will provide the sampling frame for the selection of the obstetric units. These mapping data are being collected as part of the Birthplace Research Programme in collaboration with the Healthcare Commission review of maternity services and will be available in October 2007 (20).

Ethics and R&D Approvals

Relevant approvals will be sought and achieved before data collection begins.

Outcomes

Primary outcome

Composite outcome* of neonatal mortality and morbidity: stillbirth after presentation in labour, early neonatal death (within 7 days of birth), neonatal encephalopathy, meconium aspiration, brachial plexus injury, fractured humerus or clavicle.**

Secondary outcomes

Interventions during labour:

- Syntocinon augmentation
- Epidural or spinal
- General anaesthetic
- Normal birth
- Immersion in water for pain relief
- Active management of the third stage

Neonatal outcomes:

- Stillbirth after presentation in labour
- Apgar score <7 at 5 minutes
- Early neonatal death (within 7 days of birth)
- Neonatal encephalopathy
- Meconium aspiration
- Brachial plexus injury
- Fractured humerus***
- Fractured clavicle***
- Fractured skull**
- Cephalohaematoma
- Cerebral haemorrhage
- Early onset neonatal sepsis (within 48 hours of birth)
- Kernicterus
- Seizures
- Admissions to neonatal unit within 48 hours of birth for at least 48 hours with evidence of feeding difficulties or respiratory distress

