**Note: Using a composite outcome will give the study more power to detect differences in safety between planned place of birth than if a single outcome, which would have a lower incidence, was used. The results could be misleading if the exposure affects different outcomes in different ways. For example, if the effect of planned place of birth in a particular setting decreased deaths but resulted in increased significant morbidity there might be no difference observed in the primary outcome, even though deaths were being prevented in one setting. The likelihood of this occurring is small and therefore the increased statistical power of using a composite outcome outweighs the alternative approach of substantially increasing the sample size to address individual components of the primary outcome.*

***Note: The signs of mild encephalopathy can be subtle; hence a number of such babies are likely to have a range of non-specific signs such as respiratory difficulty and poor feeding rather than features more specifically associated with encephalopathy. Since this is a mature group of babies, any difference in the incidence of these "other" admissions is likely to result from differences in the incidence of perinatal asphyxia.*

****These outcomes refer to diagnosed fractures. Minor fractures, particularly of the clavicle, are often missed and have little or no clinical significance. These fractures will not be specifically sought by this study as the aim is to collect data routinely recorded in medical records.*

Maternal outcomes:

- Maternal death (within 42 days of giving birth)
- Mode of birth: spontaneous vaginal birth (cephalic/breech presentation), instrumental vaginal birth or caesarean section
- Episiotomy
- Third or fourth degree perineal trauma
- Blood transfusion
- Breastfeeding initiation
- Admission to Intensive Therapy Unit /High Dependency Unit

Data collection

Collection of accurate and consistent information on all women giving birth in each setting during the study period is needed to calculate a reliable estimate of the adverse outcome incidence. Routine data collection systems are not fit for this purpose because of the variety of hospital information systems in use, inconsistencies in definitions between maternity systems and poor population coverage.

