The primary outcome for the national study is a composite outcome of neonatal mortality and morbidity likely to be related to the quality of intrapartum care: stillbirth after presentation in labour, early neonatal death (within 7 days of birth), neonatal encephalopathy, meconium aspiration, brachial plexus injury, fractured humerus or clavicle. The incidence of this composite outcome in women judged to be at “low risk” when presenting in labour has been used to determine the sample size needed for the national study to have adequate power to detect clinically important differences in outcome by planned place of birth. Fortunately, major neonatal and maternal morbidity in women judged to be at “low risk” at term are rare. The incidence of neonatal encephalopathy at term is approximately 1.8 per 1,000 live births (24). However, the incidence of intrapartum stillbirth after labour onset, early neonatal death and other related neonatal morbidity at term is much less certain. A reasonable estimate of the incidence of the composite measure of any neonatal morbidity, the primary outcome for the study, is 3.6 per 1,000 births. As the vast majority of data on neonatal morbidity are from obstetric units, this estimate is assumed to be the incidence of the composite outcome in obstetric units.

In order to have adequate power to detect important clinical differences in outcome that are associated with planned place of birth, the national study will need to collect data on at least 20,000 ‘low risk’ women planning to give birth in an obstetric unit, at least 17,000 women planning to give birth at home and at least 5,000 women planning to give birth in each type of midwifery unit.

Obstetric Units

Since most births in England occur in obstetric units, the national study will collect data from more women planning to deliver in this setting than any of the other settings in order to increase the statistical power of the study. We will aim to collect data on at least 20,000 women planning to give birth in an obstetric unit, who are considered to be at ‘low risk’ of complications at labour onset. As not all women who plan to give birth in an obstetric unit are considered to be ‘low risk’, we will collect data on approximately 30,000 women planning birth in obstetric units, in order to achieve the sample size of at least 20,000 ‘low risk’ women. Data will be collected from a stratified random sample of 28 obstetric units for approximately 3 months in each unit.

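### The only stated gestation limit, 36 completed weeks in obstetric units, does not match the term planning rate or the mature-baby premise used to interpret neonatal admissions

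*Protocol*

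**What the plan says.** **Eligibility (Protocol, Inclusion criteria).** The obstetric-unit group leaves out "Women who present in labour before 36 completed weeks gestation". The rule for the other three groups opens "Data will be collected for all women planning birth at home, in freestanding midwifery units and in alongside midwifery units who are attended by a" and then requires only midwifery attendance in labour at the planned place, with no gestation limit.

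**Planning rate (Protocol, Sample size considerations).** The section starts from the statement that "major neonatal and maternal morbidity in women judged to be at “low risk” at term are rare". It then says: "The incidence of neonatal encephalopathy at term is approximately 1.8 per 1,000 live births". It describes the other components at term as much less certain, and takes as a reasonable estimate that the composite, "the primary outcome for the study, is 3.6 per 1,000 births", in obstetric units.

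**Interpretation (Protocol, Outcomes).** One of the 15 neonatal secondary outcomes is "Admissions to neonatal unit within 48 hours of birth for at least 48 hours with evidence of feeding difficulties or respiratory distress". The note on mild encephalopathy justifies reading it as a marker of perinatal asphyxia: "Since this is a mature group of babies, any difference in the incidence of these" admissions is likely to come from asphyxia.

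**Analysis sets (Protocol, Secondary Objectives and Analysis).** The primary comparison is limited to women at low risk under NICE criteria that were still awaiting publication. One secondary objective compares neonatal mortality and morbidity for all women whatever their risk. Gestation at delivery is a core data item.

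**The concern.** Nowhere does the protocol say that term or maturity begins at 36 weeks. In the usual sense of term, 37 completed weeks, a baby born at 36+0 to 36+6 is eligible but is neither part of the planning population nor covered by the maturity premise.

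The admission outcome is the most exposed. Feeding difficulty and respiratory distress are signs for which immaturity is an obvious rival explanation to asphyxia. The protocol sets that rival aside by asserting maturity, and its eligibility limit does not secure it. If the share of 36-week births differs between settings, a difference in gestation could be read as a difference in intrapartum safety, which is the study's central question.

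This is separate from the limit being stated for obstetric units only. A 36-week limit applied to all four groups would still leave the three statements out of line.

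**Working it through.** **1. Is the sample-size arithmetic itself at fault? No.** Inputs from Sample size considerations: 20,000 low-risk obstetric-unit women at p₁ = 3.6 per 1,000; 17,000 home births at p₂ = 5.7 or 2.0 per 1,000; 5,000 births per midwifery-unit type at 6.8 or 1.2 per 1,000; 5% significance, taken as two-sided. With continuity correction:

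power = Φ{ [ |p₁ − p₂| − ½(1/n₁ + 1/n₂) − 1.96·SE₀ ] / SE₁ }, where SE₀ uses the pooled proportion and SE₁ the separate ones.

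For home at 5.7 per 1,000: |p₁ − p₂| = 0.0021; correction = ½(1/20,000 + 1/17,000) = 0.0000544; pooled proportion = (72 + 96.9)/37,000 = 0.004565; SE₀ = 0.000703; SE₁ = 0.000716. So z = (0.0020456 − 0.0013783)/0.000716 = 0.93 and power = 82.4%.

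| Comparison | Stated | Reproduced |
|---|---|---|
| Home, 5.7 | 82% | 82.4% |
| Home, 2.0 | 80% | 79.7% |
| Midwifery unit, 6.8 | 80% | 80.5% |
| Midwifery unit, 1.2 | 80% | 80.1% |

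The stated figures hold. The problem is which babies they describe.

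**2. Where do 36-week births enter?**

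| Comparison | Low-risk filter | 36-week obstetric-unit births |
|---|---|---|
| Primary composite | NICE criteria, content not given | Unknown |
| Secondary outcomes in low-risk women, including admissions | Same criteria | Unknown |
| Neonatal mortality and morbidity, all women | None | Eligible |

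**3. How large could the distortion be?** The protocol gives neither the share of 36-week births nor their excess risk, so everything in this step is assumed. Let s₁ and s₀ be the shares of 36-week births in the obstetric-unit and comparison groups, and R the risk at 36 weeks relative to term. With no true effect of setting, the spurious obstetric-to-other ratio is

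[1 + s₁(R − 1)] / [1 + s₀(R − 1)].

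- Admissions, s₁ = 2%, s₀ = 0.5%, R = 5: 1.08/1.02 = 1.06.
- Admissions, s₁ = 4%, s₀ = 0.5%, R = 7: 1.24/1.03 = 1.20, an apparent relative risk of 0.83 for the other setting.
- Composite, s₁ = 2%, s₀ = 0.5%, R = 2: 1.02/1.005 = 1.01.
- Composite, s₁ = 4%, s₀ = 0.5%, R = 3: 1.08/1.01 = 1.07.
- Equal shares, or a filter that removes these births: 1.00.
- Shares reversed (s₁ = 0.5%, s₀ = 2%, R = 5): 1.02/1.08 = 0.94, so the bias changes sign.

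**4. What does a term-only limit cost?** The 3.6 per 1,000 already comes from a discussion of term births, so no new planning rate is needed. If 1–5% of the 20,000 low-risk obstetric-unit women (200 to 1,000) are dropped and not replaced, the same formula gives 82.2–81.4% for home at 5.7, 79.5–78.8% for home at 2.0, 80.4–80.0% for a midwifery unit at 6.8 and 80.0–79.6% at 1.2.

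**The case against.** The strongest reply is that the 36-week rule governs data collection, not analysis. The study deliberately collects about 30,000 obstetric-unit records to obtain 20,000 low-risk women, and the NICE criteria may remove 36-week births from every low-risk comparison. The term-based planning rate concerns only low-risk women, while the all-women comparison, where these births are eligible, has no planning rate. That objective also uses the label the protocol gives to the composite, so the between-setting comparison of admissions is most naturally read as low-risk only. **This stands.** A reader might infer that the primary analysis or its power is compromised; the document does not show it.

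A reader might also infer that the mismatch must flatter home and midwifery units. It need not. Those groups have no gestation limit, so births at 36 weeks, and earlier, are not barred there. The shares that produce the bias are assumed. **This stands too.**

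The composite effect is small beside the detectable home difference of 5.7/3.6 = 1.58, and brachial plexus injury, fractures and meconium aspiration are not obviously prematurity events. Power for 5.7 per 1,000 at home could be pushed down to 44.1%, but only with a 5% share, five-fold composite risk and no such births at home. Nothing in the protocol supports that combination.

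Finally, the protocol collects gestation, leaves room to adjust for further factors, and promises a detailed analysis plan. This answers less. Gestation is not among the named adjusters, and adjustment would not make the maturity statement true of the eligible babies. The point concerns a stated threshold that disagrees with two other statements, not a detail left for later.

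**Conclusion.** The mismatch is real and lies in the protocol's own text: a 36-week limit in one group, none in the other three, a planning rate from term births, and an interpretation that presumes maturity. It rests on term having its usual meaning, since the protocol defines neither term nor maturity.

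What is established is limited. Births at 36+0 to 36+6 are eligible for the all-women neonatal comparison; their presence in the low-risk analyses cannot be settled from this document. The direction of bias is not shown. If such births concentrate in obstetric units, the other settings would look safer, with a ratio of about 1.00–1.07 for the composite and 1.00–1.20 for admissions under the assumed shares and risks. It is worth correcting because the remedy is cheap and the admission outcome depends on the premise; it does not undermine the stated sample size.

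**What to change.** Apply one limit of 37 completed weeks to all four groups for the neonatal comparisons. Either amend Inclusion criteria or keep collection as it is and restrict the analysis on recorded gestation. The second route changes no data collection. Eligibility, the planning rate and the note on mild encephalopathy would then refer to the same babies.

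The cost is a small loss of records: at the assumed 2–4% share, 600 to 1,200 of about 30,000 obstetric-unit records. Power falls by about 1 point or less if 1–5% of low-risk obstetric-unit women are dropped. At the assumed 0.5% share, the 36-week records lost elsewhere would be about 85 of 17,000 at home and 25 of 5,000 in each midwifery-unit type; any earlier births would add to these. The all-women neonatal comparison would become one of all women at 37 weeks or more, and should be described that way.

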Detailed information will be collected for every eligible woman giving birth during the study period using specially designed data collection forms. The following core data items to be collected will be the same for each planned place of birth:

Demographic data

- Mother's full name
- Mother's date of birth
- Mother's NHS number
- Mother's address including postcode
- Mother's age
- Mother's ethnicity
- Mother's understanding of English language
- Mother's marital status
- Mother's BMI
- Baby's NHS number

Obstetric details

- Mother's medical history
- Mother's obstetric history
- Gestation at delivery

Process data

- Date of delivery
- Transfer data

Maternal and infant outcomes

- Mode of onset of labour

- Mode of birth
- Perineal trauma (Episiotomy, 3rd and 4th degree trauma)
- Outcome of pregnancy (live/stillbirth)
- Sex of baby
- Birthweight of baby
- Apgar score at 5 minutes
- Postnatal maternal transfer
- Maternal blood transfusion
- Initiation of breastfeeding
- Neonatal transfer
- Neonatal morbidity
- Early neonatal death (within 7 days of birth)

Organisational data

A number of organisational and staffing factors are known to impact on the quality of care women receive. Checks will be made on changes to overall midwifery and medical staffing since the mapping data were collected. Within each trust, detailed data will be collected prospectively on throughput, staffing and outcomes at discharge. This will allow us to look at case-mix and outcomes directly linked with staffing and organisation on a day-to-day basis using methods similar to those successfully employed in the National Sentinel Caesarean Section Audit (NSCSA) (21) and the UK Neonatal Staffing Study (22). This will involve completing labour ward logs twice a day in all freestanding midwifery units, alongside midwifery units and the stratified sample of obstetric units, selected on the basis of the size and geographic location data provided by the mapping study. Staff will be asked to complete data sheets daily at specified times logging staffing levels and availability, admissions, transfers, and discharges.

Local co-ordinating midwives (LCMs)

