The only personally identifying information that will be returned to the NPEU will be the woman's postcode. The post code will be used to generate an index of multiple deprivation score for each woman. A measure of deprivation is important because if it is related to planned place of birth and having an adverse outcome it could be an important confounding factor that should be controlled for in the analysis. An application will be submitted to the Patient Information and Advisory Group (PIAG) in order to gain permission to collect women's postcode without asking for their consent to participate in the study (23). If approval is not granted by PIAG women's postcode will not be collected.

The outcomes for women and their babies who are transferred from their planned place of birth during or after labour will also be collected. This is important as these births are more likely to be associated with adverse outcomes. When a woman is transferred, the attending midwife will ensure the data form goes with the woman and that remaining data items are completed. The process of collecting these data will rely on the participation of midwives and occasionally neonatologists. Working with LCMs and, for example, the supervisors of midwives and heads of midwifery, a system to validate maternal and neonatal outcomes collected in the Birthplace forms will be developed, implemented and assured in each Trust. This will build on existing risk management reporting systems.

Completed data collection forms will be sent by midwives collecting data to their LCM. In order to ensure data quality, LCMs will validate data content and completeness, checking the maternity case notes if necessary. Also, to ensure all planned home births are included, the LCM will compare the number of forms received with appropriate local records, including records of planned home births, delivery suite and theatre registers and records of transfers to obstetric care. The LCM will detach and retain the front page and send the rest of the data collection form to the data management company for double data entry. The front page of the data collection forms will be retained by the LCMs and will be stored in a locked filing cabinet for at least 5 years or, if longer, the duration of time specified by local NHS Trust R&D procedures. LCMs will liaise with the relevant R&D departments in their Trust to ensure secure storage of these data.

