The detailed analysis plan will be formally agreed by the Co-investigator Group, with input from the Advisory Group, before data collection starts. Initially, the outcomes and characteristics of the women who planned birth in each setting will be described. Odds ratios will be calculated to compare outcomes by planned place of birth using the obstetric unit women as the comparison group. All women will be analysed by the setting in which they first received care from a health professional during labour, if that was their planned place of birth. Appropriate referral and transfer is an important element of the quality of care received by women. It is therefore important to count women in the group where they planned to give birth, regardless of where the birth actually took place.

The primary outcome of neonatal mortality and morbidity, for women considered to be at 'low risk' of complications at labour onset, will be compared by planned place of birth. The criteria set out in the NICE Intrapartum Care Guidelines, which are due for publication in September 2007, will be used to assess whether a woman would be defined as "low risk" at the onset of labour (30). Crude odds ratios will be calculated, each with a 95% confidence interval. Outcomes for each group (home, freestanding midwifery unit and alongside midwifery unit) will be compared with outcomes for women planning birth in an obstetric unit. These crude odds ratios will be adjusted in a regression model, to take account of potential confounders such as parity, age, deprivation score and other factors which may be associated with planned place of birth and adverse outcomes in pregnancy.

The secondary outcomes will be analysed in the same way as the primary outcome. Odds ratios calculated for the secondary outcomes will be presented with 99% confidence intervals. Since a large number of comparisons will be made it is important to use wider confidence intervals to reduce the likelihood of finding statistically significant associations by chance.

Crude odds ratios will be calculated comparing outcomes for women who transferred from each setting to the women who did not transfer from that setting, with 99% confidence intervals. These crude odds ratios will be adjusted in a regression model, to take account of potential confounders such as parity, age, deprivation score and other factors which may be associated with planned place of birth and adverse outcomes in pregnancy.

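### The transferred-versus-not-transferred odds ratios pool transfers before and after birth, leave the outcomes unrestricted and select confounders by a criterion that is constant within each setting

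*Protocol*

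**What the plan says.** The fourth secondary objective compares neonatal and maternal outcomes for women who transfer from home or from either type of midwifery unit "during or immediately after labour, with outcomes for women who are not transferred". Under Tools and systems for data collection, the protocol says that outcomes for women and babies "transferred from their planned place of birth during or after labour will also be collected".

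The Analysis section turns this into a within-setting contrast: "Crude odds ratios will be calculated comparing outcomes for women who transferred from each setting to the women who did not transfer". The intervals are set at the 99% level. The section does not separate transfers by timing or limit the outcomes. The crude odds ratios are then adjusted for "potential confounders such as parity, age, deprivation score and other factors", the last of these being described as "factors which may be associated with planned place of birth and adverse outcomes in pregnancy". The same adjustment wording is used for the main comparison between settings.

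The core data items list general transfer data and, separately, "Postnatal maternal transfer" and neonatal transfer. Indication and timing of transfer are to be examined, but only among women who transferred.

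**The concern.** Three features of the stated rule distort the contrast, each by a different mechanism.

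1. **Post-birth transfers.** The exposure can follow the outcome. A woman moved after birth because of a severe tear counts as transferred because the outcome happened.
2. **Unrestricted outcomes.** The maternal outcomes include caesarean section, blood transfusion and ITU/HDU admission. At home or in a freestanding unit these can be expected almost only after transfer, so women who were not transferred contribute few or no events.
3. **Confounder criterion.** Each contrast is made within one planned setting, where planned place of birth is the same for every woman. Association with it cannot identify a confounder of that contrast. The relevant criterion is association with transfer and with the outcome.

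At stake is one secondary objective. Large odds ratios, presented as adjusted, could be read as harm from transfer when much of their size comes from the definitions.

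**Working it through.** The protocol gives no figure for this contrast, so there is nothing to reproduce. The check asks what odds ratio the stated definition yields when transfer has no effect.

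**Part 1: post-birth transfers**

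Inputs:
- t, share transferred in labour, unrelated to the outcome: 43%, the protocol's upper figure for home (Birth at Home, under Sample size considerations). The values 20% and 10% are assumed.
- q, share of the remaining women with the outcome who are transferred after birth: 25%, 50%, 80% and 95%, all assumed.
- s, share of the remaining women without the outcome who are transferred after birth: 3%, assumed.

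The outcome risk cancels, so the result is the same for a rare or a common outcome:

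OR = {[t + (1 − t)q] / [t + (1 − t)s]} ÷ {(1 − q) / (1 − s)}

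For t = 0.43 and s = 0.03, t + (1 − t)s = 0.43 + 0.57 × 0.03 = 0.4471. For q = 0.50, t + (1 − t)q = 0.43 + 0.57 × 0.50 = 0.715. Then OR = (0.715 / 0.4471) ÷ (0.50 / 0.97) = 3.1.

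| t | q = 25% | q = 50% | q = 80% | q = 95% |
|---|---|---|---|---|
| 43% | 1.7 | 3.1 | 9.6 | 42.2 |
| 20% | 2.3 | 5.2 | 18.2 | 83.1 |
| 10% | 3.3 | 8.4 | 31.3 | 145.9 |

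The true odds ratio is 1.0 throughout. With q = s = 3% the formula returns 1.0, so the excess comes entirely from outcome-driven transfer. If only in-labour transfers count as exposed, and women transferred after birth stay in the comparison group, the odds ratio is also 1.0.

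**Part 2: near-empty cells**

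Take the protocol's 17,000 planned home births, 43% in-labour transfer and its general figure of 0.5% for transfusion. That gives 17,000 × 0.43 = 7,310 transferred, 17,000 − 7,310 = 9,690 not transferred, and 17,000 × 0.005 = 85 transfusions.
- If 5 of the 85 fall among women not transferred: OR = (80 × 9,685) / (7,230 × 5) = 21.4.
- If 1 does: OR = (84 × 9,689) / (7,226 × 1) = 112.6.
- If none does, the odds ratio is not finite.

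The splits of 5, 1 and 0 are assumed. The 43% is an upper figure that excludes post-birth transfers, and the 0.5% is not specific to planned home births. The example shows only how far the result depends on a few events.

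**Part 3: confounder criterion**

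No arithmetic applies. The contrast compares women who transferred with women who "did not transfer from that setting, with 99% confidence intervals", while the adjustment sentence asks for "other factors which may be associated with planned place of birth and adverse outcomes in pregnancy". The first fixes the setting; the second selects covariates by their association with setting.

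**The case against.** The strongest reply is that this is analysis-plan detail. The protocol defers to a detailed plan to be agreed before data collection, records postnatal maternal transfer separately, and forbids neither a split by timing nor reporting sparse cells as counts. The objective is to compare, the protocol makes no causal claim for these odds ratios, and it says in advance that transferred births are more likely to have adverse outcomes. This limits the weight of the point but does not remove it. The protocol already states the pooled exposure and the confounder criterion, and a plan that follows it inherits both. Adjusting for confounders also invites more than a descriptive reading.

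Other parts of the defence stand:
- A reader might infer that these odds ratios as a whole measure reverse causation. The text does not support that. The term fits only post-birth transfers prompted by the outcome. In-labour transfers raise confounding by indication, and hospital-only outcomes raise a structural problem.
- A reader might infer that the covariates are wrong. Parity, age and deprivation are reasonable, and the list is open. Only the selection criterion fails.
- Epidural, general anaesthetic and augmentation are listed as interventions, whereas the transfer objective names neonatal and maternal outcomes, so they are not clearly in scope.
- The exposure is transfer of the woman. A sick baby illustrates the problem only when the mother is moved too.

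**Conclusion.** The concern holds in limited form. As stated, the rule lets the outcome cause the exposure for post-birth transfers, includes outcomes with almost no chance of occurring without transfer from home or a freestanding unit, and selects confounders by a factor that is constant within each contrast.

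With no effect of transfer, the first feature alone gives odds ratios of about 1.7 to 42 at the protocol's upper in-labour transfer figure, and higher values at lower assumed figures. These sizes rest on assumed post-birth transfer shares and are illustrations, not predictions. The near-empty cells are inferred from the nature of the outcomes, since the protocol does not say that they occur only after transfer. The inference is weaker for alongside units, which share a site with an obstetric unit. An infinite odds ratio should therefore not be presented as a certain result.

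Nor should a reader carry the point over to the main safety comparison. Women there are analysed by planned place of birth wherever the birth takes place, so it is unaffected.

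**What to change.** Amend the transfer paragraph of the Analysis section as follows.

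1. Separate transfers before birth from transfers after birth, using the transfer items already collected.
2. Estimate odds ratios for before-birth transfers only, and only for outcomes that can arise in both groups, listed by setting. Keep women transferred after birth in the comparison group. Dropping them would remove cases selectively: with the assumed q = 50% and s = 3%, the odds ratio under no effect would be 0.97 / 0.50 = 1.94.
3. Report post-birth transfers and hospital-only outcomes as counts and percentages, so that the stated objective is still covered in full.
4. Define confounders as factors associated with transfer and with the outcome: parity, age, deprivation, gestation, and medical and obstetric history. All are already planned for collection, deprivation subject to the approval needed for postcodes.
5. State that the in-labour odds ratios are descriptive, because confounding by indication remains after this adjustment.

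The cost is fewer odds ratios and slightly more analysis work. No new data are needed.
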